10.1 Regulatory, ethical and research oversight considerations

10.1.1 Informed consent

Patients must sign an informed consent form before participating in the trial. During the trial, the rights and interests of patients must be ensured, and patient information must be kept confidential in accordance with GCP requirements.

According to the Helsinki Declaration and the GCP requirements of the State Food and Drug Administration, written informed consent must be obtained before the patient enters the trial, that is, before blood samples are collected for screening assessment or any other research-related activities. The researcher is responsible for fully and comprehensively introducing the purpose of the study, the effects of the drug, possible toxic and side effects, and possible risks to the subjects or their designated

representatives, and should let the subjects know their rights, the risks and benefits to be assumed, and give the subjects a copy of relevant information. Then, give the subjects sufficient time to consider the content of this study in order to decide whether to participate. Conversational communication is a very important informed consent process. If the subject and his legal representative are illiterate, the informed consent process should be witnessed by the subject or his legal representative, who should sign the informed consent form after verbal consent, and the witness's signature should be on the same day as the subject's signature.

Each subject must obtain a written informed consent in duplicate, one copy is given to the subject and the other is retained by the researcher.

This clinical trial must comply with the Declaration of Helsinki (1996 edition), Good Clinical Practice (GCP) issued by CFDA, and related regulations. Before the start of the trial, the clinical research institution's ethics committee must be approved before the study can begin. During the clinical trial, any changes to this trial protocol must be reported to the ethics committee and filed.

10.1.2 Study suspension and termination

If there are sufficient reasonable reasons, this study may be temporarily suspended or terminated early. The party that suspends or terminates the study should notify the subjects and researchers in writing and record the reasons for the suspension or termination of the study. If the study is terminated or suspended early, the principal investigator (PI) should promptly notify the subjects and the Institutional Review Board (IRB) and provide the reasons for the termination or suspension of the study.

Circumstances that may require termination or suspension include, but are not limited to:

- Determination of unexpected, significant, or unacceptable risks to subjects;
- Demonstration of effectiveness provides justification for cessation;
- Insufficient compliance with protocol requirements;

- Data are incomplete and/or insufficient for evaluation;
- Determination that the primary endpoint had been met;
- Determine that the study is invalid.

The study may proceed only if issues related to safety, protocol compliance, and data quality are addressed.

11. References

[2] Rustgi, Anil K, and Hashem B El-Serag. "Esophageal carcinoma." The New England journal of medicine vol. 371,26 (2014): 2499-509.

[3] Domper Arnal, María José et al. "Esophageal cancer: Risk factors, screening and endoscopic treatment in Western and Eastern countries." World journal of gastroenterology vol. 21,26 (2015): 7933-43.

[4] Yu, Canqing et al. "Hot Tea Consumption and Its Interactions With Alcohol and Tobacco Use on the Risk for Esophageal Cancer: A Population-Based Cohort Study." Annals of internal medicine vol. 168,7 (2018): 489-497.

[6] Wang Lili, Wang Jian, Yu Bo, Liu Huilan, Hu Lijun, Zhou Juying. Analysis of toxic and side effects of radiotherapy and prognostic factors in elderly patients with esophageal cancer[J]. Chinese Journal of Oncology Prevention and Treatment, 2018, 25(23): 1638-1642.

[7] Jiang, Dongxian et al. "The prognostic value of EGFR overexpression and amplification in Esophageal squamous cell Carcinoma." BMC cancer vol. 15 377. 8 May. 2015.

12.1 ECOG performance status scoring standard

Physical condition ECOG scoring standard Zubrod-ECOG-WHO (ZPS, 5 points)

Fitness score	Physical status
0	The ability to move is completely normal, with no difference from the ability to move before the onset of the disease
1	Able to move around freely and engage in light physical activities, including general housework or office work, but not able to engage in heavy physical activities
2	Able to move around freely and take care of oneself, but has lost the ability to work and can be out of bed and active for at least half of the day.
3	He can only partially take care of himself and spends more than half of the day in bed or in a wheelchair.
4	Bedridden and unable to take care of oneself
5	Die

12.2 Response Evaluation Criteria for Solid Tumors Version 1.1

(Response Evaluation Criteria in Solid Tumors RECIST Version 1.1)

1. Tumor measurability at baseline

1.1 Definition

At baseline, tumor lesions/nodes were categorized as measurable or non-measurable based on the following definitions:

1.1.1 Measurable lesions

Tumor lesions: There is at least one accurately measurable diameter (recorded as the maximum diameter), the minimum length of which is as follows:

- CT scan 10 mm (CT scan layer thickness is no more than 5 mm)
- Routine clinical examination instruments: 10 mm (tumor lesions that cannot be accurately measured with caliper instruments should be recorded as unmeasurable)
- Chest X-ray 20 mm
- Malignant lymph nodes: pathologically enlarged and measurable, the short diameter of a single lymph node on CT scan must be ≥ 15 mm (the CT scan layer thickness is recommended to be no more than 5 mm). During baseline and follow-up, only the short diameter is measured and followed up.

1.1.2 Non-measurable lesions

All other lesions, including small lesions (longest diameter < 10 mm or pathological lymph node short diameter ≥ 10 mm to < 15 mm) and lesions that cannot be measured. Lesions that cannot be measured include: meningeal disease, ascites, pleural or pericardial effusion, inflammatory breast cancer, skin/lung lymphangitic carcinomatosis, abdominal masses that cannot be diagnosed and followed up by imaging, and cystic lesions.

1.1.3 Special considerations for lesion measurement

Bone lesions, cystic lesions, and lesions previously treated with local therapy require special mention:

Bone lesions:

- Bone scans, PET scans, or plain radiographs are not suitable for measuring bone lesions, but can be used to confirm the presence or absence of bone lesions;
- Osteolytic lesions or mixed osteolytic/osteoblastic lesions with a definite soft tissue component that meets the above definition of measurability can be considered measurable lesions if they can be evaluated using cross-sectional imaging techniques such as CT or MRI.
- Osteogenic lesions are non-measurable lesions.

Cystic lesions:

- Lesions that meet the definition of simple cysts on radiographic imaging should not be considered malignant lesions because they are simple cysts by definition. They are neither measurable lesions nor non-measurable lesions.
- If the metastatic lesion is cystic and meets the above definition of measurability, it can be considered a measurable lesion. However, if there is a non-cystic lesion in the same patient, the non-cystic lesion should be selected as the target lesion.

Topically treated lesions:

- Lesions located in areas that have been irradiated or treated with other locoregional therapies are generally considered non-measurable unless there is clear progression of the lesion. The study protocol should describe in detail the conditions under which these lesions are considered measurable.

1.2 Description of measurement method

1.2.1 Lesion measurement

During clinical evaluation, all tumor measurements should be recorded in metric units. All baseline assessments of tumor lesion size should be completed as close to the start of treatment as possible and must be completed within 28 days (4 weeks) before the start of treatment.

1.2.2 Evaluation methods

The same techniques and methods should be used for baseline assessment and subsequent measurements of lesions. All lesions must be evaluated using imaging, except for lesions that cannot be evaluated by imaging but can only be evaluated by clinical examination.

Clinical lesions: Clinical lesions are considered measurable only when they are superficial and have a diameter of ≥ 10 mm (such as skin nodules). For patients with skin lesions, it is recommended to use color photos with a ruler to measure the size of the lesion for archiving. When lesions are evaluated by both imaging and clinical examination, imaging should be used as much as possible because it is more objective and can be reviewed repeatedly at the end of the study.

Chest X-ray: When tumor progression is an important research endpoint, chest CT should be used first because CT is more sensitive than X-ray, especially for new lesions. Chest X-ray is only applicable when the measured lesion has clear boundaries and the lungs are well ventilated.

CT, MRI: CT is currently the best available and repeatable method for evaluating efficacy. The definition of measurability in this guideline is based on CT scan slice thickness ≤ 5 mm. If the CT slice thickness is greater than 5 mm, the minimum measurable lesion should be twice the slice thickness. MRI is also acceptable in some cases (such as whole body scans).

Ultrasound: Ultrasound should not be used as a measurement method to measure lesion size. Ultrasound examinations are not repeatable after the measurement is completed due to their operation dependence, and the consistency of technology and measurement between different measurements cannot be guaranteed. If new lesions

are found using ultrasound during the trial, CT or MRI should be used for confirmation. If the radiation exposure of CT is considered, MRI can be used instead.

Endoscopy, laparoscopy: These techniques are not recommended for objective tumor evaluation, but they can be used to confirm CR when biopsy specimens are obtained and to confirm recurrence in trials where the endpoint is recurrence after CR or surgical resection.

Tumor markers: Tumor markers cannot be used alone to evaluate objective tumor response. However, if the marker level exceeds the upper limit of normal at baseline, it must return to normal levels to evaluate complete response. Because tumor markers vary from disease to disease, this factor must be taken into account when writing measurement standards into the protocol. Specific criteria for CA-125 response (recurrent ovarian cancer) and PSA (recurrent prostate cancer) response have been published. In addition, the International Gynecologic Cancer Organization has developed CA-125 progression criteria, which will soon be added to the objective tumor evaluation criteria for first-line ovarian cancer treatment.

Cytology/histology techniques: These techniques can be used to identify PR and CR in specific circumstances specified in the protocol (e.g., residual benign tumor tissue is often present in lesions of germ cell tumors). When effusions may be a potential side effect of a therapy (e.g., treatment with taxane compounds or angiogenesis inhibitors) and the measurable tumor meets the criteria for response or stable disease, the appearance or worsening of tumor-related effusions during treatment can be confirmed by cytology techniques to distinguish between response (or stable disease) and progressive disease.

2 Tumor response assessment

2.1 Assessment of total tumor and measurable lesions

To evaluate objective response or possible future progression, it is necessary to perform a baseline assessment of the total tumor burden of all tumor lesions as a reference for subsequent measurements. In clinical protocols with objective response

as the primary treatment endpoint, only patients with measurable lesions at baseline can be included. Measurable lesions are defined as the presence of at least one measurable lesion. For trials with disease progression (time to disease progression or degree of progression on a fixed date) as the primary treatment endpoint, the protocol inclusion criteria must clearly state whether only patients with measurable lesions are included, or whether patients without measurable lesions can also be included.

2.2 Baseline Recording of Target and Non-target Lesions

When there is more than one measurable lesion at baseline, all lesions should be recorded and measured, with a total of no more than 5 lesions (no more than 2 per organ) as target lesions representing all involved organs (that is, patients with only one or two involved organs should select a maximum of two or four target lesions as baseline measurement lesions).

Target lesions must be selected based on size (longest diameter), representative of all involved organs, and measurements must be reproducible. Sometimes when the largest lesion cannot be reproducibly measured, a reselection of the largest lesion that can be reproducibly measured is appropriate.

Lymph nodes are of particular concern because they are normal tissue and can be detected on imaging even without metastasis. Pathological lymph nodes, defined as measurable nodules or even target lesions, must meet the following criteria: a short diameter of ≥ 15 mm on CT. Only the short diameter is required at baseline. Radiologists often use the short diameter of a nodule to determine whether the nodule has metastatic disease. Nodule size is generally expressed in two dimensions detected by imaging (axial plane for CT and one of the axial, sagittal, or coronal planes for MRI). The short diameter is the smallest value. For example, a 20 mm \times 30 mm abdominal nodule has a short diameter of 20 mm and can be considered a malignant, measurable nodule. In this example, 20 mm is the measurement of the nodule. Nodules with a diameter of ≥ 10 mm but < 15 mm should not be considered target lesions. Nodules < 10 mm do not fall into the category of pathological nodules and do

not need to be recorded or further observed.

The sum of the diameters of all target lesions (including the longest diameter of non-nodal lesions and the short diameter of nodal lesions) will be reported as the baseline diameter sum. If lymph node diameters are included, as mentioned above, only the short diameter will be included. The baseline diameter sum will be used as a reference value for the baseline level of disease.

All other lesions, including pathological lymph nodes, can be considered non-target lesions and do not need to be measured, but should be recorded at the baseline assessment, such as "present", "absent" or, in rare cases, "definitely progressed". Extensive target lesions can be recorded together with the target organ (such as extensive enlargement of pelvic lymph nodes or massive liver metastases).

2.3 Remission criteria

2.3.1 Target lesion assessment

Complete remission (CR): All target lesions disappear and the short diameter of all pathological lymph nodes (including target nodules and non-target nodules) must be reduced to <10 mm.

Partial response (PR): The sum of the target lesion diameters decreases by at least 30% compared with the baseline level.

Disease progression (PD): The minimum value of the sum of all target lesion diameters measured during the entire experimental study is used as a reference, and the relative increase in the sum of diameters is at least 20% (if the baseline measurement value is the smallest, the baseline value is used as a reference); in addition, the absolute value of the sum of diameters must increase by at least 5 mm (the appearance of one or more new lesions is also considered disease progression).

Stable disease (SD): The reduction in target lesions has not reached the level of PR, nor has the increase in target lesions reached the level of PD, but is somewhere in between. The minimum value of the sum of diameters can be used as a reference for

research.

2.3.2 Precautions for target lesion assessment

Lymph nodes: Even if the lymph nodes identified as target lesions are reduced to less than 10 mm, the actual short diameter value corresponding to the baseline must be recorded for each measurement (consistent with the anatomical plane at the baseline measurement). This means that if the lymph nodes are target lesions, even if the criteria for complete remission are met, it cannot be said that the lesions have disappeared, because the short diameter of normal lymph nodes is defined as <10 mm. Target lymph node lesions must be specifically recorded in a specific location on the CRF form or other recording method: for CR, all lymph node short diameters must be <10 mm; for PR, SD, and PD, the actual measurement of the target lymph node short diameter will be included in the sum of the target lesion diameters.

Target lesions too small to measure: In clinical studies, all lesions (nodular or non-nodular) recorded at baseline should have their actual measurements recorded again at subsequent evaluations, even if they are very small (e.g., 2 mm). However, sometimes they are so small that the CT scan image is very blurry and the radiologist has difficulty defining the exact value, so they may be reported as "too small to measure." In this case, it is important to record the previous value on the CRF. If the radiologist believes that the lesion may have disappeared, it should also be recorded as 0 mm. If the lesion is indeed present but is too blurry to give an accurate measurement, a default value of 5 mm can be used. (Note: This is unlikely to occur with lymph nodes, as they are generally of measurable size under normal circumstances or are often surrounded by fat tissue as in the retroperitoneum; however, if this situation occurs and a measurement cannot be given, a default value of 5 mm is also used.) The default value of 5 mm is derived from the cut thickness of the CT scan (this value does not change with different cut thickness values of CT). Since the chance of the same measurement being repeated is unlikely, providing this default value will reduce the risk of incorrect assessment. However, it needs to be reiterated that if the radiologist can give an exact numerical value for the lesion size, the actual

value must be recorded even if the lesion diameter is less than 5 mm.

Separate or coalesced lesions: When a non-nodular lesion is fragmented, the longest diameters of the separate parts are added together to calculate the sum of the diameters of the lesion. Similarly, for coalesced lesions, the planes between the coalesced parts can be distinguished and the maximum diameters of each are calculated. However, if the lesions are inseparable, the longest diameter should be the longest diameter of the entire coalesced lesion.

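### Appendix 12.2 gives conflicting CRF values for a target lesion that is too small to measure, so one scan can be scored stable disease or partial response (minor)

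*Protocol*

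**What the plan says.** Protocol Appendix 12.2 reproduces response criteria and is where CR, PR, SD and PD are defined. Inclusion criterion 5 (section 5.1) refers to it, and section 8.1.1 uses progression without defining it separately.

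Item 2.3.2 covers target lesions so small that "the CT scan image is very blurry and the radiologist has difficulty defining the exact value". It then gives three instructions:

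- general: "In this case, it is important to record the previous value on the CRF";
- the lesion may have disappeared: "it should also be recorded as 0 mm";
- the lesion is still there: "If the lesion is indeed present but is too blurry to give an accurate measurement, a default value of 5 mm can be used".

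The reason given for the default is that "providing this default value will reduce the risk of incorrect assessment". The item also asks for the true figure whenever the radiologist can give one, even below 5 mm.

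Item 2.3.1 uses the sum of diameters twice. PR is defined as: "The sum of the target lesion diameters decreases by at least 30% compared with the baseline level". For PD, "The minimum value of the sum of all target lesion diameters measured during the entire experimental study is used as a reference", and the sum must rise by at least 20% and at least 5 mm above it.

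**The concern.** The first and third instructions cover the same situation, a small blurred lesion with no exact value, and give different numbers for the same CRF field. Nothing says which takes precedence, and the 5 mm default is worded as optional. Carrying the last value forward also works against the stated purpose of the default, because it records no change where there was marked shrinkage.

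Two endpoints use this field. ORR (secondary) depends on the change from baseline, so a carried-forward value can turn a responder into stable disease. PFS (primary, investigator-assessed under section 9.1) depends on the smallest sum recorded, so a carried-forward value can set that reference too high and delay recorded progression. The first error understates ORR and the second lengthens PFS. DCR is unaffected by a switch between SD and PR.

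**Working it through.** The protocol states no figure on this point, so there is nothing to reproduce. The check applies its own rules to assumed lesion sizes.

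**Rules used**
- PR if sum ≤ 0.70 × baseline (item 2.3.1).
- PD if sum ≥ 1.20 × nadir and sum − nadir ≥ 5 mm, so the PD threshold is the larger of 1.20 × nadir and nadir + 5 mm (item 2.3.1). The nadir is the smallest sum on study.
- A single target lesion is enough for entry (section 5.1, criterion 5).
- After the week-9 review, imaging is every 12 weeks (84 days; section 4.1.4).

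**Step 1: one scan, one target lesion, 30 → 22 mm → too small but present**

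| Value entered | Change from 30 mm | Category | Nadir | PD threshold at that point |
|---|---|---|---|---|
| previous, 22 mm | 22/30 − 1 = −27% | SD | 22 mm | max(26.4, 27) = 27 mm |
| default, 5 mm | 5/30 − 1 = −83% | PR | 5 mm | max(6, 10) = 10 mm |

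If the lesion is judged gone and entered as 0 mm, the target-lesion result is CR.

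**Step 2: does the high nadir persist?** Assume regrowth from 5 mm with volume doubling time D days, so diameter = 5 × 2^(t/(3D)), scanned every 84 days. The doubling times are assumptions. A measured value below 22 mm becomes the new nadir.

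| D (days) | Scans at 84, 168, 252 days (mm) | PD, 5 mm rule (threshold 10) | PD, previous-value rule | Delay |
|---|---|---|---|---|
| 30 | 9.5, 18.2 | day 168 | nadir 9.5, threshold 14.5: day 168 | 0 |
| 45 | 7.7, 11.9, 18.2 | day 168 | nadir 7.7, threshold 12.7: day 252 | 84 days |
| 60 | 6.9, 9.5, 13.2 | day 252 | nadir 6.9, threshold 11.9: day 252 | 0 |

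84 days is 84/30.4 = 2.8 months. If the lesion stays unmeasurable up to 7, 8 or 10 mm, the delay at these three doubling times is still at most one scan. A narrow band in between can give two. At D = 55 days with 7.1 mm still unreadable, the next values are 10.1, 14.4 and 20.5 mm. The 5 mm rule calls PD at 10.1 mm (day 168). The previous-value rule then has nadir 10.1 and threshold 15.1, and calls PD at 20.5 mm (day 336).

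**Step 3: is the response lost?** For a 30 mm baseline, PR needs 21 mm or less. The first regrowth values in the table (9.5, 7.7 and 6.9 mm) are 68%, 74% and 77% below baseline, so PR is recorded then. It stays lost if the lesion remains present but unmeasurable, or is never again measured at 21 mm or less.

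**Step 4: more than one lesion**
- Two lesions, 30+20 → 25+16 → too small+16: previous value 41/50 = −18% (SD); default 21/50 = −58% (PR); nadir 41 against 21.
- Five 20 mm lesions, each 18 mm at the previous scan, one then too small: 90/100 = −10% against 77/100 = −23%, SD either way; nadir 90 against 77, about 1.2 times.
- One lesion, 40 → 25 → too small: PR was already met at 25 mm (−37.5%), so only the nadir differs.

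**The case against.** The strongest reply is that the item resolves itself. Two specific cases follow the general sentence, only the default is given a reason, and the item asks for actual measurements throughout. The previous value might be meant as a note kept beside the entry, and an experienced reader of scans may use 0 or 5 mm anyway. This makes correct use likely, but the text neither calls the previous value a side note nor ranks the instructions.

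The reply on size is stronger, and most of it stands.

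- **Progression.** A reader might infer that progression must wait for 27 mm. In the example that would mean delays of 2.8 to 8.3 months. The protocol does not support this: item 2.3.1 takes the minimum over the whole study, so the first real measurement below 22 mm replaces the carried-forward reference.
- **ORR.** A reader might infer that every such scan removes a responder. Item 2.4.3 takes the best response over all time points, and item 2.6.1 does not require confirmation when progression is the primary endpoint, so a later measurement can restore PR. The schedule (section 1.3, footnote 2) also requires imaging within a week after radiotherapy, when a shrinking lesion may be measured at 21 mm or less before it becomes unreadable.
- **What remains.** A lesion that stays present but unmeasurable, after a sum short of −30%, is still scored SD instead of PR. These are patients with marked and lasting shrinkage.

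**Conclusion.** The wording is wrong as it stands: one situation has two recording rules, and following the first gives a wrong sum. The severity is minor.

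- **Single scan:** −27% (SD) against −83% (PR) in the one-lesion example.
- **ORR:** a responder is lost only if the earlier sum was short of −30% and the lesion is never again measured at or below that level.
- **PFS:** target-lesion progression is recorded about zero to one 12-week scan late (0 to 2.8 months) in affected patients. This rests on assumed doubling times of 30 to 60 days and on the lesion being measured once it regrows; two scans needs the narrow combination shown above. Progression by new or non-target lesions is untouched.

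The protocol does not give the share of patients affected, so no shift in ORR or median PFS can be derived from it. Against the planned gain of 18.2 − 16 = 2.2 months, the effect on the median is probably small, because few patients are likely to meet all the conditions and the delay in each is short. A reader might infer that the primary endpoint is materially biased; the documents do not support that. Treating 0/5 mm as the intended rule rests on the reason the item itself gives for the default.

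**What to change.** In Appendix 12.2, item 2.3.2:

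1. Replace the instruction to record the previous value with: *a value must be recorded on the CRF at that assessment: the actual measurement if one can be given, 0 mm if the lesion is judged to have disappeared, otherwise 5 mm.*
2. Make the default mandatory by changing *can be used* to *is used*.
3. State that earlier values are not carried forward into the sum of diameters or the nadir.

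The cost is a short wording change and a matching CRF completion note. Any entry already made by carrying a value forward needs correcting, and the response category and nadir that depend on it need re-deriving. No extra scans, patients or staff are required.
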